- 1) To evaluate the safety, tolerability, and adverse event profile of ponatinib in patients with advanced lung cancer.
- 2) To determine the progression free survival (PFS), pattern of failure (CNS vs. extra-CNS) and response duration (in patients who achieve an objective response) of ponatinib in molecularly defined cohorts of patients with advanced lung cancer treated at the ‘biologically selected dose’.
- 3) To compare the ORR in biomarker positive cohorts to the FGFR1 double negative cohort.

Tertiary/Exploratory:

- 1) To explore additional molecular mechanisms of initial sensitivity and resistance to ponatinib in patients with advanced lung cancer, including but not limited to addressing the impact of higher cutpoints/alternate patterns of FGFR1 copy number by SISH and mRNA levels by ISH on maximal percentage shrinkage per RECIST or PFS or duration of response in the FGFR1 copy number and/or mRNA positive cohorts; and the impact of FGF2 and/or 9 ligand mRNA levels by ISH on maximal percentage shrinkage per RECIST or PFS or duration of response in FGFR1 copy number and/or mRNA positive cohorts.
- 2) To explore the molecular mechanisms of acquired resistance to ponatinib in patients with advanced lung cancer who initially benefited (minor or objective responses, or stable disease ≥ 6 months on therapy) but then progressed, including but

not limited to looking at changes in tumor or host biology comparing pre-treatment with available post-progressing tumor and/or other biological samples.

Eligibility Criteria (Prescreening) Part A

Inclusion Criteria

1. Patients must have histologically confirmed metastatic lung cancer (any histology, except carcinoid) stage IV (according to the 7th edition of the AJCC staging manual).
2. Existing formalin fixed paraffin embedded biopsy of the lung cancer with potentially sufficient material for analysis.
3. NSCLC with adenocarcinoma histology must have been previously tested for both EGFR mutations and ALK rearrangements (cf Exclusion point 1 below).
4. Able (physically and financially) to travel to University of Colorado for clinical trial treatment.

Exclusion Criteria

1. Known EGFR mutation and/or ALK rearrangement in NSCLC with adenocarcinoma histology.
2. Patients aged <18 years of age.

Eligibility Criteria (Intervention Trial) Part B

Inclusion Criteria

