5.1 Rationale for web-based outreach and remote consenting

[figure not shown]
One of the biggest challenges to conducting a biomarker pre-selected clinical trial in lung cancer is the identification and capture of sufficient marker positive patients to populate the trial within a reasonable time frame. In adenocarcinoma alone, which represents approximately 40% of the NSCLC histology in the US based on SEER database figures, the most common molecular subtype may only be present in ~20% of cases and the rarest in <1% (Owonikoko et al, 2007; Kris et al, 2011). When only a very small number of academic centers in the USA see >1000 new NSCLC patients annually, and not all of these patients will have the appropriate stage, fitness or motivation to be considered for a clinical trial, trials exploring markers present in a small percentage of the lung cancer population simply cannot reasonably be conducted based on the local catchment of even several trial sites anymore. Beyond the needs of investigators, new approaches are required to address the needs of patients in the wider community. Specifically, for those who wish to take advantage of the potential breakthroughs in personalized medicine that are happening in lung cancer, but who don't wish to travel to an academic center simply to sign the consent form for trial specific molecular pre-testing, when their chances of a positive result are slim. Although we did not employ remote consenting at the time, our previous experience with using one consent form for the initial ALK testing, followed by separate consenting for treatment of those patients proven to be ALK positive (ALK+) within the early company-sponsored crizotinib trials, suggests remote consenting would be feasible for widespread trial-specific biomarker prescreening (Kwak et al, 2010). Remote consenting would involve the patient having the molecular prescreening consent discussed over the phone and the signed consent faxed or emailed back, the tumor specimen would then be sent to us for testing, with the patient only travelling to us to screen for the treatment aspects of the trial if the subsequent biomarker result was positive.

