5.2.1 Eligibility Criteria (Prescreening) Part A

Inclusion Criteria

1. Patients must have histologically confirmed locally advanced (after failure of local therapy) or metastatic lung cancer (any histology, except carcinoid) stage IIIa, IIIb or IV (according to the 7th edition of the AJCC staging manual).
2. Existing formalin fixed paraffin embedded biopsy of the lung cancer with potentially sufficient material for analysis.
3. NSCLC with adenocarcinoma histology must have been previously tested for both EGFR mutations and ALK rearrangements (cf Exclusion point 1 below).
4. Able (physically and financially) to travel to University of Colorado for clinical trial treatment.

Exclusion Criteria

1. Known EGFR mutation and/or ALK rearrangement in NSCLC with adenocarcinoma histology.
2. Patients aged ≤ 18 years of age are not eligible for screening.

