2009; Camidge et al, 2010; Weickhardt and Camidge, 2011). We have also shown that different oncogenic drivers, such as ALK rearrangements or EGFR mutations, are associated with different patterns of metastatic spread at diagnosis (Doebele, Lu et al, 2012). Finally, while the association of specific drivers with sensitivity to specific targeted therapies is now well known, we and others have also recently shown that these markers may also be associated with differential sensitivity to certain specific standard chemotherapies such as a carboplatin/paclitaxel doublet or pemetrexed (Mok et al, 2009; Camidge et al, 2011; Lee et al, 2011). Patients who sign the consent for trial-specific molecular prescreening (locally or remotely) will have the features that will ultimately be associated with either positive and negative biomarker results recorded directly and confirmed by medical note review. These factors will include but not be limited to age at diagnosis of current lung cancer, age at diagnosis of metastatic lung cancer (if different), sex, race, histology, current stage, sites of metastatic disease at diagnosis, smoking status, other known molecular features such as EGFR, KRAS and ALK status and overlap of any trial specific positive biomarker results, and home State. In addition, the consent will permit retrospective and prospective data capture relating to the patient's prior therapies and outcomes from these therapies (response and progression free survival (noting the method and frequency of radiographic assessment)), patterns of metastatic spread and overall survival from the date of diagnosis of metastatic disease. We will then analyze both the clinical and demographic features associated with positivity, as well as any suggestion of a marker specific responsiveness/non-responsiveness to specific standard therapies as we have done before (Camidge et al, 2010; Camidge et al, 2011; Doebele, Lu et al, 2012). We will compare and contrast these with the data available from the largely resection based cases of the TMAs we are also analyzing. Responsiveness to ponatinib will be assessed within Part B.

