Based on our experiences with several different biomarker selected trials in lung cancer, we anticipate approximately 50% of the screening enrollments to come from outside Colorado. This is feasible during the time scale of the study given our prior experience with *ALK*, but excessive use of screening resource on groups with low/no marker positive prevalence is undesirable if we wish to make maximum use of the available support. We have adopted some enrichment policies upfront, assuming *RET* changes will be mutually exclusive with *FGFR1* biomarkers, and similarly that all of these will be mutually exclusive with *EGFR* mutations and *ALK* rearrangements in adenocarcinomas. These assumptions will be tested in a TMA analysis and if the TMA data suggest that a significant proportion of marker positive patients are being missed by any of these approaches, we will adapt our strategy accordingly. As the coordinating center for the LCMC, the vast majority of our adenocarcinoma patients and most other histologies have already been profiled by *ALK/ROS1/MET* FISH and by SNaPshot analyses. The initial high *RET* positivity rate in our BJALCF funded project, looking in cases that are ‘pan-negative’ on these platforms, continues to suggest that mutual exclusivity predominates for most of the known oncogenic drivers in lung cancer. However, the existing clinical/TMA dataset for *FGFR1* biomarkers is less mature than for *RET* and we have already noted overlap with *KRAS* mutations in some cell lines. Consequently, beyond the exclusion of known *ALK+* or *EGFR* mutant adenocarcinomas, we have not mandated further enrichment strategies for *FGFR1* screening. Yet, for internal cases, to maximize yield we will continue to prioritize cases ‘pan-negative’ on our standard platforms for testing with *RET* FISH within this study. This means internally, we may not complete *RET* FISH testing on some *FGFR1* double negatives because of the presence of other known molecular drivers. Beyond capturing the molecular test results already conducted on each case, we will not be able to determine whether external cases have been similarly prioritized for any aspect of the screening or not. Because our internal cases are likely to have been more extensively profiled than those in the community, we have estimated a higher *RET* positivity rate for the patients we screen internally compared to those sent through the remote prescreen consenting process. Because we do not know the degree to which ‘pan-negatives’ will be prioritized for the *FGFR1* testing internally, or the overlap of *FGFR1* related biomarkers with most of the known oncogenic drivers in lung cancer, we have not assumed any specific alteration in marker positivity for internal as opposed to external cases. However, as data emerge, we will consider formally instituting practical enrichment for *FGFR1* biomarkers, ruling out some subgroups to screen if ≥ 100 patients of a

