6.1 Inclusion Criteria

1. Patients must have histologically confirmed locally advanced (after failure of local therapy) or metastatic lung cancer (any histology, except carcinoid) stage IIIa, IIIb or IV (according to the 7th edition of the AJCC staging manual).

2. Patients must be proven to meet marker criteria (FGFR1 SISH+ISH+, FGFR1 SISH+ISH-ve, FGFR1 SISH-veISH+, FGFR1 SISH-veISH-ve (FGFR1 double negative cohort) or RET FISH+) prior to enrollment into Part B (treatment) using one of the assays described in Appendix A. Adenocarcinoma patients must be known to not possess either an EGFR mutation or an ALK rearrangement in their tumor (if positive for one, testing for both is not required).

2. Patients must have measurable disease as per RECIST version 1.1.

3. Patients must have received prior platinum-based chemotherapy but may have received any number of other lines of prior therapy.

4. Age \geq 18 years.

5. Life expectancy of \geq 3 months.

6. ECOG performance status \leq 2 (Karnofsky \geq 60%; see Appendix B).

7. Patients must have normal organ and marrow function as defined below:

- | | |
|-----------------------------|--|
| - leukocytes | \geq 3,000/mcL |
| - absolute neutrophil count | \geq 1,500/mcL |
| - hemoglobin | \geq 9 g/dL |
| - platelets | \geq 100,000/mcL |
| - total bilirubin | \leq 1.5 x institutional upper limit of normal (ULN),
unless due to Gilbert's syndrome |
| - AST(SGOT)/ALT(SGPT) | \leq 2.5 X ULN |
| - creatinine | \leq 1.5 X ULN |
| OR | |
| - creatinine clearance | \geq 60 mL/min/1.73 m ² for patients with creatinine
levels above institutional normal |
| - serum lipase and amylase | \leq 1.5 X ULN |

8. Previous treatment related side-effects/adverse events must have resolved to at least grade 1 or, at the discretion of the investigator, select stable grade 2 toxicities (e.g. alopecia or fatigue) may be permissible if unchanging in grade for at least 3 months following discussion with the PI.

9. Patients with CNS metastases are eligible for enrollment if they have no overt evidence of neurological deficits, and are not requiring anti-epileptics or steroids to control their neurological symptoms. Patients with known CNS metastases must have relevant CNS imaging performed approximately coincident with body imaging during response assessments.

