10.2 Part A Analysis Plan

The goal of Part A is to determine the prevalence of each biomarker and the overlapping frequency of biomarkers (primary objective), which will guide on-going screening for selecting biomarker positive patients for the clinical trial to be conducted in part B. The association between biomarker positivity and the patient clinical and pathological features will be studied (secondary objective) to guide the selection process. In addition, the effectiveness of prescreening locally and nationally will be estimated (secondary objective). Interim analyses will be conducted after 250 and 500 screened samples, before the final analysis, to inform ongoing screening strategies. We will compare and contrast these with the data available from planned and ongoing analyses of tissue microarrays. With 700 samples, the maximum width (distance from the lower limit to the higher limit) of 95% confidence interval for the prevalence of a biomarker will be 0.075.

Biomarker prevalence and its 95% (exact) confidence interval (CI) among the screening patients and for different histologies will be reported. Overlapping frequency and its 95% CI between biomarkers among the screening patients and for different histologies will also be reported. The association between biomarker positivity and clinical/pathological features will be assessed using chi-square test, or Fisher's exact test if necessary, with the features including histology, age at diagnosis of current lung cancer (using age groupings as a categorical variable where necessary), age at diagnosis of metastatic lung cancer, race, sex, current stage, sites of metastatic disease at diagnosis, smoking status, EGFR, KRAS and ALK status. Biomarker prevalence will be reported for each category of features significantly

associated with biomarker prevalence. We will determine the impact of biomarker results on prognosis generating Kaplan-Maier survival curves for overall survival using log-rank testing to compare the survival distributions between marker positive and negative patients for each biomarker. In addition, we will determine the impact of the biomarker results on sensitivity or resistance to standard chemotherapies and patterns of metastatic spread as we have done before (Camidge et al, 2011; Doebele et al, 2012).

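### Overall survival by marker in Part A has no stated origin or risk-set entry date, so curves drawn from metastatic diagnosis would count death-free time before consent, and ponatinib exposure has no rule

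*Combined protocol and SAP*

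**What the plan says.** Section 10.2 (repeated in the Study Synopsis, Part A Analysis Plan) sets out to determine the effect of biomarker results on prognosis, with Kaplan-Meier OS curves and "using log-rank testing to compare the survival distributions between marker positive and negative patients for each biomarker". It names no origin and no entry date. Section 10.4 defines PFS and response duration but not OS.

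The origin appears only in the data-capture text of the Synopsis, Section 1, Section 4 and Section 5.3, where consent covers "overall survival from the date of diagnosis of metastatic disease". Observation starts at consent. Section 5.1 describes this for remote patients: "Remote consenting would involve the patient having the molecular prescreening consent discussed over the phone". Section 5.2 has case notes acquired after consent. Earlier history is collected retrospectively, but only for patients who lived to consent.

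On referral route, Section 5.5 expects a higher RET "positivity rate for the patients we screen internally compared to those sent through the remote prescreen consenting process". For FGFR1 markers it says "we have not assumed any specific alteration in marker positivity for internal as opposed to external cases".

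Section 5.3 aims to describe natural history separately from responsiveness to ponatinib, and leaves responsiveness to Part B.

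On stage, Section 5.2.1 admits "stage IIIa, IIIb or IV (according to the 7th edition of the AJCC staging manual"), whereas the Part A prescreening criteria in the Synopsis say "Patients must have histologically confirmed metastatic lung cancer (any histology, except carcinoid) stage IV".

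**The concern.** A patient who dies between metastatic diagnosis and Part A consent cannot be in the dataset. If survival is counted from diagnosis and everyone is placed at risk from that date, the interval up to consent adds time at risk but no deaths. The interval need not be short: Part A requires an existing biopsy and, for adenocarcinoma, completed EGFR and ALK testing. Part B, where Part A patients are headed, adds "Patients must have received prior platinum-based chemotherapy".

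Two further gaps bear on the marker comparison. If the delay differs between marker-positive and marker-negative patients, the log-rank test compares groups with different amounts of death-free time. And marker-positive patients are treated with ponatinib more often by design, while Section 10.2 does not say how treated patients enter an analysis meant to be separate from ponatinib response.

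At stake is the natural-history output of Part A: marker-specific survival could be reported as longer than it is.

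**Working it through.** **The plan's own figures.** The only precision figure in Section 10.2 is the maximum 95% interval width for prevalence, 0.075. The exact interval at 350/700 has width 0.0754, so it reproduces. Nothing comparable is given for OS. Table 10 sums to the stated 700 screened and 266 RET-tested.

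**Curves.** The protocol gives no delay, so all delays are assumed. Let S(t) be true survival from diagnosis and let the delay A be uniform on 0 to 2m months (mean m), unrelated to survival, with complete follow-up. Only patients with T > A are seen. For t ≥ 2m the unadjusted curve is S(t)/S̄, where S̄ is the mean of S over 0 to 2m (the share who live to consent). The unadjusted median solves S(t) = 0.5 × S̄. Two shapes, both with true median 10 months:

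- Exponential, λ = ln 2/10 = 0.0693, S̄ = (1 − e^(−2mλ))/(2mλ). At m = 3, S̄ = 0.818 and the median is −ln(0.409)/0.0693 = 12.9. At m = 6, S̄ = 0.679 and the median is 15.6.
- Two-stage (mean 5 months to progression, then mean 7 to death), S(t) = (7e^(−t/7) − 5e^(−t/5))/2. At m = 3, S̄ = 0.895 and the median is 11.1. At m = 6, S̄ = 0.727 and the median is 12.9.

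So the overstatement is about 1.1 to 2.9 months at mean delay 3, and 2.9 to 5.6 at mean delay 6. In both settings, delayed entry at consent returns about 10.0.

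**When consent depends on prognosis.** Take the two-stage model. Let a fraction of patients consent within 1 month of progression, with delay uniform on 0 to 6 months for the rest. True median 10.0:

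| Fraction at progression | Unadjusted | Delayed entry |
|---|---|---|
| 0 | 11.1 | 10.0 |
| 25% | 10.9 | 9.0 |
| 50% | 10.8 | 7.8 |
| 75% | 10.6 | 6.5 |

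**Log-rank test.** From Table 10:

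- RET+ is 14 internal + 6 external = 20. RET-tested negatives are 56 + 190 = 246. Internal share is 70% against 23%.
- SISH+ is 46 internal and 45 external. ISH+ is 67 and 66. Route is balanced.

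Simulated type I error for RET (nominal 5%, true median 12 months, 4,000 runs per setting), by assumed mean delay: about 5% with equal delays of 6 months; about 9% with internal 3 and external 6; about 12% with internal 3 and external 9; about 5% with external shorter (internal 6, external 3). The delayed-entry log-rank gives 5 to 6% throughout. At 3 against 9 months by route, SISH and ISH give 6% and 5%.

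**Planned ponatinib exposure, initial cohorts** (Section 10.1 cohort sizes over Table 10 totals):

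- RET+ 13/20 = 65%; RET-tested negatives 22/246 = 9%, counting all 22 double-negative patients as RET-tested.
- SISH+ (13 + 13)/91 = 29%; SISH− (13 + 22 + 13)/609 = 48/609 = 8%.
- ISH+ 26/133 = 20%; ISH− 48/567 = 8%.

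Section 10.1 allows up to 36 more patients, likely mostly double negative. If all 36 were, the negative shares become up to 58/246 = 24%, 84/609 = 14% and 84/567 = 15%.

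**The case against.** The strongest reply is that the obvious remedy can do more harm than the plan. Prior platinum is required for Part B, and Part A patients must be able to travel for trial treatment, so consent around treatment failure is plausible. If half consent at progression, delayed entry gives 7.8 months against a true 10.0, while the unadjusted curve gives 10.8. This stands: delayed entry should be neither the only nor the lead method. Part A itself does not require prior therapy, so the share who consent at progression is unknown.

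It can also be said that the flaw is read from silence, since Section 10.2 never says that the curves start at diagnosis. That is fair as far as it goes, but no other OS origin appears anywhere, and following the text leads to the problem.

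A reader might infer that the RET log-rank test is inflated. The 9% and 12% need external patients to consent later than internal ones, which the protocol nowhere states; in the reverse order the test keeps its size. Nor do the documents support a material SISH or ISH distortion by route. A reader might also take 22/246 as a ceiling on exposure in RET negatives; the extra 36 patients show that it is not.

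**Conclusion.** The concern holds in limited form. Section 10.2 leaves the OS origin and risk-set entry undefined, and the only origin elsewhere in the protocol makes time before consent count as time at risk. If delay is unrelated to survival, the curves read high: for a true median of 10 months, by about 1 to 3 months at mean delay 3 and about 3 to 6 at mean delay 6. The delays, the true median and the survival shapes are all assumptions.

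Distortion of the log-rank test is a possibility, mainly for RET, and not a demonstrated fault. The missing rule for ponatinib-treated patients is a real gap against the aim in Section 5.3, but the direction of any effect on OS is unknown and the exposure gap could narrow.

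A reader might infer that the trial's main results are compromised. They are not: OS by marker is not a listed objective and carries no decision rule, and prevalence, overlap and ORR are untouched. The change is worth making because it is cheap, not because a primary conclusion depends on it.

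**What to change.** In Section 10.2:

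1. Report OS by marker from the Part A consent date, so that no time before observation is counted.
2. If OS from metastatic diagnosis is also reported, enter patients into the risk set at consent (left-truncated Kaplan-Meier, delayed-entry log-rank or Cox). Show numbers at risk and the unadjusted curve beside it, and state that delayed entry is biased downward if patients consent at progression.
3. Tabulate time from diagnosis to consent, and from last progression to consent, by marker and by internal or external route, so that readers can judge which case applies.
4. Compare RET only among RET-tested patients.
5. Add a sensitivity analysis that censors at first ponatinib dose, or fits ponatinib as a time-dependent covariate, noting that both are open to selection of fitter patients.

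Separately, the Synopsis and Section 5.2.1 must be reconciled on stage III eligibility, so that the metastatic-diagnosis origin is defined for every patient.

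The cost is SAP wording and modest programming. Section 5.3 already captures the diagnosis date and prior-therapy outcomes, and the study holds consent and first-dose dates. The downsides are wider intervals, small early risk sets under delayed entry, and a RET estimate that stays imprecise under any method with 20 expected positives. OS from consent also answers a different question from OS from diagnosis, and the report should say so.
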